Using this choice of truncation parameter, the higher of the two Level 4 p-values will be evaluated at a 3.75% significance level (2-sided). If it is significant at the 3.75% level, then both hypotheses H04a and H04b will be rejected, and testing will proceed to Level 5. If it is not significant at the 3.75% level, then the lower of the 2 Level 4 p-values will be evaluated at a 2.5% significance level (2-sided). If it is significant, then the relevant null hypothesis (either H04a or H04b) will be rejected, and testing will proceed to Level 5. If it is (also) not significant, then formal testing will stop at Level 4. The significance levels for subsequent evaluation in Level 5 for each of these scenarios are given below.

Level 5

[figure not shown]
The null hypothesis H05 will be tested at the significance level retained from Level 4, which depends on the outcomes in Level 4 as follows:

- Case 1: If both comparisons in Level 4 exhibit statistical significance, then H05 will be tested at a 2-sided 5% significance level with regard to change from baseline in weekly mean ASD score.
- Case 2: If only one of the comparisons in Level 4 exhibits statistical significance, then H05 will be tested at the 2-sided significance level $\alpha - [\gamma\alpha + (1-\gamma)\alpha/2]$ retained from Level 4, where $\alpha = 0.05$.

Using the proposed choice of $\gamma = 0.5$, if both H04a and H04b were rejected in Level 4, then H05 in Level 5 will be tested at a 2-sided 5% significance level (Case 1). If only one of H04a and H04b was rejected in Level 4, then H05 in Level 5 will be tested at a 2-sided 1.25% significance level (Case 2).

The multiple testing procedure is summarised graphically in the following figure:

Figure 1 Multiple testing procedure

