Unstructured covariance will be assumed to model the relationship between pairs of response variables taken at different visits on the same subject. To allow for the possibility that the MMRM model fails to converge with unstructured covariance, the following hierarchical approach is proposed to select a simpler covariance structure if the preceding covariance structure fails to converge: Unstructured → Heterogeneous Toeplitz → Heterogeneous First Order Autoregressive → Toeplitz → First Order Autoregressive → Compound Symmetry. Before concluding non-convergence at any step of this hierarchy, an attempt will first be made to resolve convergence problems by using different starting values of the underlying algorithm and/or adjusting singularity options. The Kenward-Roger approximation to estimating the degrees of freedom will be used for tests of fixed effects derived from the MMRM model.

For the ASD endpoint, each of the 52 weeks used for weekly mean calculation will replace visit in the above model specification.

Descriptive summaries of the key secondary endpoints will also be presented.

Adjusted means from the MMRM model above will be displayed graphically over time and used to evaluate time of onset of effect. Adjusted means will be calculated from the MMRM using the observed margins approach, in which the contribution of model factors to the estimate is weighted proportionally to the presence of these factors in the data.

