4.2.5.4 Supporting analyses

As a supportive analysis to the analysis of change from baseline in ACQ-6, the main ACQ-6 analysis described in [Section 4.2.5.1](#) will be repeated for change from baseline in ACQ-5 and ACQ-7 score using a similar MMRM model. Similar descriptive and graphical summaries will also be produced.

The analysis of AQLQ(S)+12 total score change from baseline will be repeated for change from baseline in each of the 4 AQLQ(S)+12 domain scores using a similar MMRM model.

The analysis of ACQ-6 score change from baseline will be repeated for change from baseline in each of the 6 individual ACQ-6 items using a similar MMRM model.

As further supportive analyses to the analyses of change from baseline in ACQ-6, AQLQ(S)+12 and weekly mean ASD, responders/non-responders will be summarised descriptively and analysed using a generalised linear model for repeated measures, using a logit link function. The response variable in the model will be the binary responder status at each scheduled post-randomisation visit up to and including Week 52, irrespective of whether the subject remained on treatment and/or took other treatments. Treatment, visit, region, age (adolescents or adults) and treatment by visit interaction will be included as factors in this model. Baseline of the corresponding endpoint will also be included in the model as a continuous linear covariate.

In this model, inference will be based on generalised estimating equations (GEEs) using the method of [Liang and Zeger \(1986\)](#). An unstructured working correlation matrix will be used, along with empirically corrected standard errors. For the ASD responder endpoint, each of the 52 weeks used for weekly mean calculation will replace visit in the above model specification.

Only the first (responder/non-responder) ACQ-6 and AQLQ(S)+12 definitions in [Section 3.2.3.3](#) will be analysed using the repeated measures GEE analysis. The other categorical definitions in this section will be summarised descriptively only.

Change from baseline in the percentage of asthma symptomatic days (as defined in [Section 3.2.3.5](#)) will be summarised for the on-study period for each post-baseline week using descriptive statistics.

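### If the 52-week unstructured model for the Asthma Symptom Diary (ASD) test, H05, fails to converge, the fallback covariances carry model-based standard errors that can be too small at Week 52

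*SAP*

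**What the plan says.** SAP 4.1.2 and protocol 9.4.1 place H05 (change from baseline in weekly mean ASD score at Week 52) at Level 5 of a family with strong control at 0.05. It is tested at two-sided 5% if both Level 4 hypotheses are rejected, and at 1.25% if only one is.

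SAP 4.2.5.1 gives one model for all four key secondary endpoints: "Unstructured covariance will be assumed to model the relationship between pairs of response variables taken at different visits on the same subject". For ASD, "each of the 52 weeks used for weekly mean calculation will replace visit in the above model specification". Baseline enters as a single linear covariate, and a baseline-by-visit term is explicitly left out. Under SAP 3.1.1 the ASD baseline is the mean of the same diary over the week before randomisation.

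If the fit fails after new starting values or changed singularity options, a ladder is used to "select a simpler covariance structure if the preceding covariance structure fails to converge". The steps of that ladder, in order, are "Unstructured → Heterogeneous Toeplitz → Heterogeneous First Order Autoregressive → Toeplitz → First Order Autoregressive → Compound Symmetry". On inference: "The Kenward-Roger approximation to estimating the degrees of freedom will be used for tests of fixed effects derived from the MMRM model". No empirical standard error is specified for any step, and ASD has no separate provision. For the responder analyses, by contrast, SAP 4.2.5.4 says: "An unstructured working correlation matrix will be used, along with empirically corrected standard errors".

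The imputation and tipping-point analyses (SAP 4.2.5.2) refit the same model to the imputed data.

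**The concern.** A model-based standard error is right only if the assumed covariance is right. Unstructured covariance makes no assumption that can be wrong in this sense; every step below it does. Kenward-Roger adjusts for having estimated the covariance parameters, not for having chosen the wrong form. Giving each week its own variance, as heterogeneous Toeplitz and heterogeneous AR(1) do, does not protect Week 52, because the variance estimates are themselves inconsistent when the assumed correlation pattern is wrong.

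If the ASD model falls back under such a pattern, the H05 confidence interval is too short and the Level 5 error rate exceeds the level claimed. The sensitivity analyses would not reveal this, because they inherit the same covariance choice.

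**Working it through.** **1. The plan's own figure.** Inputs from SAP 1.3: 530 per arm, SD 1.3, difference 0.3. SE = 1.3 × √(2/530) = 0.0799. Power = Φ(0.3/0.0799 − 1.96) = Φ(1.80) = 96.4%. Minimum detectable difference = 1.96 × 0.0799 = 0.157. Both agree with the stated 95% or higher and 0.16.

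**2. Covariance parameters.** Unstructured, 52 weeks: 52 × 53/2 = 1,378. ACQ-6 has 14 post-baseline visits to Week 52 (Weeks 2, 4, 8, ..., 52): 14 × 15/2 = 105. ASD fallbacks: heterogeneous Toeplitz 52 + 51 = 103, heterogeneous AR(1) 52 + 1 = 53, Toeplitz 52, AR(1) 2, compound symmetry 2.

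**3. Why the residual correlation can change over time.** Suppose the raw diary is stationary with variance 1 and correlation ρ(k) at lag k, and b is the common slope on baseline. The baseline-adjusted residuals at weeks s and t have

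Cov(s,t) = ρ(|t−s|) − b·ρ(s) − b·ρ(t) + b².

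If ρ is constant (an exchangeable diary), this depends only on whether s = t, and both heterogeneous fallbacks are correct. If ρ decays, it depends on s and t separately.

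Example (assumed): random intercept 40% of variance, AR(1) part 50% with weekly correlation 0.95, noise 10%. Take b as the mean of ρ(1) to ρ(52): 0.4 + 0.5 × 0.340 = 0.570, so b² = 0.325. Here ρ(1) = 0.875, ρ(4) = 0.807, ρ(5) = 0.787, ρ(48) = 0.443 and ρ(52) = 0.435.

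- Weeks 1 and 5: covariance 0.807 − 0.570 × 1.662 + 0.325 = 0.185; SDs 0.572 and 0.654; correlation 0.49.
- Weeks 48 and 52: covariance 0.807 − 0.570 × 0.878 + 0.325 = 0.631; SDs 0.906 and 0.911; correlation 0.77.

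The lag is four weeks in both cases, but the correlation differs. No Toeplitz or AR form can represent that.

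**4. Effect on the Week 52 standard error.** For each assumed true covariance, the working structure was fitted by maximising the expected Gaussian log-likelihood, and its model-based SE was divided by the true SE to give r. Type I error = 2 × [1 − Φ(z·r)], with z = 1.96 at 5% and 2.498 at 1.25%. For example, r = 0.85 gives 2 × [1 − Φ(1.666)] = 9.6%.

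| Assumed truth | Het. Toeplitz r | Het. AR(1) r | Type I error at 5% |
|---|---|---|---|
| Exchangeable diary | 1.00 | 1.00 | 5% |
| Lag-only residual correlation, SD rising 0.65 to 1.30 | 1.000 | 1.000-1.007 | about 5% |
| Stationary diary, correlation plateaus quickly | 0.945-0.973 | 0.966-0.986 | 5.3-6.4% |
| Stationary diary, slow decay (as in step 3; intercept 20-60%, weekly correlation 0.93-0.98) | 0.85-0.91 | 0.89-0.94 | 6.7-9.7% |
| Random intercept and slope, seven settings, 0% or 10% dropout | 0.86-0.98 | 0.88-0.98 | 5.5-9.1% |

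In the random-slope settings, type I error at nominal 1.25% is 1.4-3.1%. The step 3 example sits at the mild end of its row (r = 0.91 and 0.94).

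**5. Later fallbacks.** With lag-only correlation and SD rising linearly from 0.65 to 1.30, Toeplitz, AR(1) and compound symmetry give r = 0.73-0.77 and type I error of about 13-15%. If the SD falls over time they overstate instead (r = 1.13-1.17).

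**6. Simulation check.** Steepest random-slope case (SD 0.89 at Week 1 to 1.30 at Week 52), complete data, null true, 400 trials. The empirical SD of the estimate was 0.081. Mean SE was 0.080 (unstructured), 0.070 (heterogeneous AR(1)) and 0.065 (AR(1)), with rejection rates of 5.5%, 9.3% and 12.0%. Heterogeneous Toeplitz had a mean SE of 0.069 in 60 trials, too few for a useful rejection rate.

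**The case against.** The strongest reply is that the fallback may never be used. A reader might infer from 1,378 parameters against about 1,060 subjects that failure is likely. The documents do not support that: the relevant comparison is subjects with time points, 1,060 against 52, and about 55,000 weekly means are planned (1,060 × 52 = 55,120). In three simulated trials with 10% uniform dropout and 8% intermittent missingness (assumed), an EM fit of the unstructured model converged in 12-13 iterations each time. That was not REML software with Kenward-Roger, so numerical trouble is not excluded, but the parameter count alone does not make it probable. This part stands: the probability of fallback is unknown, and every error rate above is conditional on it.

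A reader might also infer that heterogeneous Toeplitz must fail because the variance of change grows after baseline. It need not. Growth in SD alone leaves it accurate (second row of the table), and an exchangeable diary adjusted for baseline shows no growth at all. The cause is correlation that changes over time.

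Finally, the ladder is pre-specified, as protocol 9.4.3.2 requires, so there is no data-driven choice. H05 is also the last test and is reached only after Levels 1 to 3 and at least one Level 4 rejection. Both points are right. They limit the consequence but do not make the fallback standard errors valid.

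**Conclusion.** The point holds as a conditional weakness. If the ASD model leaves unstructured covariance, nothing in the SAP protects the H05 test against a wrong structure. Under the covariances examined for the first two fallbacks, the model-based Week 52 standard error is between 1.00 and about 0.85 of the true one, and type I error is between 5% and about 9-10% at nominal 5%. The favourable end applies when residual correlation depends only on lag. The unfavourable end needs raw diary correlation that decays slowly with lag, combined with the pre-randomisation week as baseline and a common slope. Both the baseline and the common slope are features of this plan.

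Every covariance here is an assumption, since the documents give no weekly standard deviations or correlations. It would go too far to say that the H05 error rate is inflated as planned: if the unstructured model converges, H05 is unaffected. The stated power is correct, and none of the other three endpoints has 52 time points. The change is worth making because it is cheap and protects a confirmatory claim.

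**What to change.** Add to SAP 4.2.5.1: if any covariance structure other than unstructured is used for a key secondary endpoint, the test and confidence interval use empirical (sandwich) standard errors, with a compatible degrees-of-freedom method (for example between-within) in place of Kenward-Roger. State that the rule carries over to the imputation, tipping-point and COVID-19 refits of the same model.

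The cost is SAP wording and the loss of Kenward-Roger for fallback fits, which matters little at about 530 per arm. Sandwich errors repair the standard error only; they do not remove possible bias from a wrong covariance when dropout is missing at random.

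Optionally, for ASD, place an unstructured fit to the means at Weeks 4, 8, ..., 52 ahead of the structured fallbacks (13 points, 13 × 14/2 = 91 parameters). Under an assumed covariance with 10% dropout, its Week 52 SE was 0.0437 against 0.0436 for the full model, a loss under 0.5%. This is a trade-off rather than a correction, because it drops the weekly adjusted means that the SAP uses to judge time of onset. The weekly model should therefore be kept for those plots.

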4.2.5.2 Sensitivity analyses

Controlled imputation

Sensitivity analyses of the repeated measures analyses will be performed for all 4 of the continuous key secondary endpoints using controlled sequential multiple imputation methods based on pattern mixture models. The multiple imputations will be done in 2 steps:

- i. The non-monotone (intermediate visits) missing values will be imputed first, assuming MAR (the Markov chain Monte Carlo [MCMC] method will be used to partially impute the data using SAS PROC MI).
- ii. Then, the remaining monotone missing values at each visit will be imputed using the sequential regression method (using the MONOTONE REG option in PROC MI). At each iteration, missing values will be imputed sequentially, one time-point at a time.

Different assumptions will be made to impute the monotone missing data:

- a. MAR: Missing data in each arm will be imputed assuming the distribution within that treatment group.
- b. MNAR/DRMI: Missing data will be imputed differently depending on the reason for study withdrawal.

Missing data for subjects in the tezepelumab arm who dropped out for a treatment-related reason will be imputed assuming the subject's whole distribution, both pre-withdrawal and post-withdrawal, is the same as the placebo arm (the "copy reference" approach), whereas the remaining subjects will be imputed assuming MAR.

Subjects with missing baseline data will be excluded from these analyses.

Table 7 summarises how tezepelumab subjects withdrawing from study will be handled in the DRMI analyses described above.

Step(a):

In Step (i) above, a single Markov chain will be used with a non-informative (Jeffreys) prior distribution. The first 200 iterations will be discarded to allow for convergence to a stationary distribution and to remove the effect of the starting values ("burn-in"). A gap of 100 iterations will be used between imputations to ensure independence between imputations ("thinning"). Convergence of the MCMC algorithm will be assessed. Non-monotone missing data are expected to be relatively infrequent.

Step(b):

The sequential monotone regression method in Step (ii) is achieved by only including selected data at each stage of the imputation. This is implemented as follows, where t represents each post-baseline visit, proceeding one visit at a time from the first post-baseline visit until the imputed dataset has complete values at all post-baseline visits. If a negative value is imputed at any time, it will be replaced with a zero value.

MNAR/DRMI

To impute missing values at time t for subjects in the tezepelumab arm who withdrew from the study for treatment-related reasons, the imputation model will use only placebo subjects who had observed data at time t ; the dataset itself also needs to include the tezepelumab subjects who withdrew for treatment-related reasons at time $t-1$, since it is these subjects for which the imputation is required.

To impute missing values at time t for all placebo subjects and tezepelumab subjects who withdrew from the study for reasons unrelated to treatment, the imputations are performed assuming MAR i.e. using an imputation model which uses subjects who had observed data at time t from within the respective treatment group. If a negative value is imputed at time t , then it will be replaced with a zero value.

For each of the MAR and DRMI analyses, 100 imputations will be carried out. A random seed of 670376 will be used for the non-monotone imputations, and a random seed of 966654 will

be used for the monotone imputations. These same random seeds will be used for the multiple imputation analyses of all 4 key secondary endpoints.

The imputation models will use absolute values of the relevant endpoint (including the baseline value). Change from baseline will then be calculated in imputed datasets. The imputation model will include the same baseline covariates as used in the main analysis model (i.e. those specified in [Section 4.2.5.1](#)).

Each of the imputed datasets will be analysed using the same MMRM model specified in [Section 4.2.5.1](#). The results from the analysis on each imputed dataset will be combined across imputations in a way which appropriately accounts for within-imputation and between-imputation variance (using the SAS procedure PROC MIANALYZE).

Tipping point analysis

A tipping point analysis will be performed for each of the four continuous key secondary endpoints, using similar multiple imputation methodology. In this analysis, various degrees of improvement in the placebo group δ_P after withdrawal, and various degrees of worsening in the tezepelumab group δ_T after withdrawal, will be simultaneously explored.

Placebo subjects who withdrew from the study (irrespective of reason for discontinuing IP) will have their first imputed value improved by δ_P . This results in a one-time shift towards a better value in the outcomes of placebo subjects that withdrew from the study after a given visit. Tezepelumab subjects who withdrew from the study (irrespective of reason for discontinuing IP) will have their first imputed value worsened by δ_T . This results in a one-time shift towards a worse value in the outcomes of tezepelumab subjects that withdrew from the study after a given visit.

Tipping points are defined as the range of smallest values (δ_P, δ_T) which would result in a change of conclusion, the latter being assessed according to the nominal statistical significance levels applied in [Section 4.1.2](#).

Step (i) will first be applied to the non-monotone missing values, exactly as specified above for control imputation.

For step (ii), the sequential monotone regression method will also be applied. To impute missing values at time t for subjects in the placebo arm, an imputation model which uses placebo subjects who had observed data at time t will be used, and the one-time improvement δ_P applied to this. To impute missing values at time t for subjects in the tezepelumab arm, an imputation model which uses tezepelumab subjects who had observed data at time t will be used, and the one-time worsening δ_T applied to this. In other words, imputation will be performed within each treatment arm, and therefore $(\delta_P, \delta_T) = (0, 0)$ corresponds to the MAR analysis.

For pre-BD FEV₁ change from baseline:

- δ_P will be varied from 0 to 0.3 L in increments of 0.1 L
- δ_T will be varied from 0 to -0.3 L in increments of 0.1 L.

If a tipping point was observed with analysis using 0.1 mL increments, smaller increments of 0.05 mL will then be explored in the relevant range to determine the tipping point more precisely.

For AQLQ(S)+12 total score change from baseline:

- δ_P will be varied from 0 to 3 in increments of 1
- δ_T will be varied from 0 to -3 in increments of 1.

If a tipping point was observed with analysis using increments of 1, smaller increments of 0.5 will then be explored in the relevant range to determine the tipping point more precisely.

For ACQ-6 score change from baseline:

- δ_P will be varied from 0 to -3 in increments of 1
- δ_T will be varied from 0 to 3 in increments of 1.

If a tipping point was observed with analysis using increments of 1, smaller increments of 0.5 will then be explored in the relevant range to determine the tipping point more precisely.

For weekly mean daily ASD score change from baseline:

- δ_P will be varied from 0 to -2 in increments of 1
- δ_T will be varied from 0 to 2 in increments of 1.

If a tipping point was observed with analysis using increments of 1, smaller increments of e.g. 0.5 may need to be explored in the relevant range to determine the tipping point more precisely.

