4.2.4.2 Sensitivity analyses

Controlled imputation

To examine the sensitivity of the results of the primary analysis to departures from the underlying assumptions about missing data, controlled multiple imputation analyses will be performed which allow for different underlying assumptions to be used.

An underlying negative binomial stochastic process for the number of exacerbations will be assumed and post-study withdrawal counts will be imputed conditional upon the observed number of events prior to the withdrawal under both MAR and missing not at random (MNAR)/dropout reason-based (DRMI) assumptions respectively:

- a) MAR: Missing counts in each arm will be imputed assuming the estimated event rate within that treatment group.
- b) MNAR/DRMI: Missing counts will be imputed differently depending on the reason for dropout.

Missing counts for subjects in the tezepelumab arm who dropped out for a treatment-related reason will be imputed based on the estimated event rate in the placebo arm (the "copy reference" approach), whereas the remaining subjects who dropped out will be imputed assuming MAR.

Table 7 summarises how tezepelumab subjects withdrawing from study will be handled in the DRMI analyses described above. The rules in the table will be applied irrespective of the length of time between discontinuing IP and withdrawing from study (noting that the treatment policy strategy is used for these sensitivity analyses).

Table 7 Treatment arms for imputation of tezepelumab subjects under DRMI

Reason for withdrawing from study	Reason for discontinuing IP	DRMI
Death		Placebo
Site terminated by sponsor		Tezepelumab
Study terminated by sponsor		Tezepelumab
Loss to follow-up Withdrawal by Subject Withdrawal by parent/guardian Other	Death	Placebo
	Adverse event	Placebo
	Development of study-specific discontinuation criteria	Placebo
	Severe non-compliance to protocol	Placebo
	Subject lost to follow-up	Placebo by default (pending blinded review of any further information)
	Subject decision	Placebo by default (pending blinded review of any further information)
	Other	Placebo by default (pending blinded review of any further information)

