A blinded review of subjects who discontinued IP for reasons of “Subject lost to follow-up”, “Subject decision” or “Other” will be performed prior to unblinding at the primary database lock. A listing of these subjects and the assumptions made under DRMI will be documented. If any recorded comments (on either of the “Discontinuation of Investigational Product” or “Disposition” eCRF pages) indicate clearly that the reason for study withdrawal was not related to treatment, then the “Placebo” default for DRMI in the above table may be changed for that subject.

The methodology used for sensitivity analysis is described in more detail in [Keene et al., 2014](#). The steps for carrying out multiple imputation are outlined below.

Step 1: Fitting a negative binomial model to the observed data

A negative binomial regression model will be fitted to the observed exacerbation data with treatment group, region, age and history of exacerbations included as covariates. The logarithm of the time at risk (in years) for exacerbation will be used as an offset variable in the model.

Step 2: Drawing samples from the posterior distribution

The negative binomial distribution is conventionally defined as the probability distribution of the number of successes Y before k failures are seen in a series of independent Bernoulli trials with probability p of success and $(1-p)$ of failure.

The posterior distribution for parameter k and coefficients β will be created as a product of non-informative prior and the likelihood from the model in Step 1. A uniform prior distribution will be assumed for the regression coefficients. A Gamma (10^{-4} , 10^{-4}) will be assumed for $1/k$.

With the use of Markov Chain Monte Carlo (MCMC) method, 100 samples of k and β will be drawn from their posterior distribution. Convergence of the MCMC algorithm will be assessed.

A random seed of 991511 will be used. The first 2000 iterations will be discarded to allow for convergence to a stationary distribution and to remove the effect of the starting values (“burn-in”). A gap of 100 iterations will be used between imputations to ensure independence between imputations (“thinning”).

Step 3: Imputing missing data

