4.2.5 Key secondary endpoints

4.2.5.1 Main analysis

The main analysis of the key secondary endpoints (changes from baseline to Week 52 for each of pre-bronchodilator FEV₁, AQLQ(S)+12 total score, ACQ-6 score and weekly mean ASD score) will quantify the effect of the initially randomised treatment at Week 52, regardless of the treatments that subjects actually received, or whether the subjects received other controller therapy/rescue medications, including for subjects who discontinued study treatment prior to Week 52.

This analysis uses a treatment policy strategy and will therefore include all available data after treatment discontinuation until the end of the planned treatment period.

Subjects will be encouraged to continue to undergo applicable study related visits/procedures for the full 52-week period even after premature discontinuation of IP. Consequently, subjects lost to follow-up, subjects who die, subjects who withdraw their consent and subjects who choose Option 3 for their follow-up should be the only source of missing information for the key secondary analyses apart from subjects who choose Option 2 for their follow-up, who will have missing pre-BD FEV₁ following discontinuing of IP until their Week 52 visit.

Missing data will be modelled based on what was observed during the study using direct likelihood approaches, which is a valid approach under the assumption that data are missing at random (MAR).

Change from baseline for the key secondary endpoints in the tezepelumab group will be compared to that seen in the placebo group using a mixed model for repeated measures (MMRM) model. This model will be used to perform the statistical tests of the null hypotheses specified in [Section 4.1.1](#), and to estimate the treatment effect at Week 52 and its 95% confidence interval, for each endpoint.

The response variable in the model will be change from baseline at each scheduled post-randomisation visit up to and including Week 52, and irrespective of whether the subject remained on treatment and/or took other treatments. Treatment, visit, region, age (adolescents or adults) and treatment by visit interaction will be included as factors in this model. Baseline of the corresponding endpoint will also be included in the model as a continuous linear covariate. Baseline by visit interaction will not be included as a covariate in the MMRM model.

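### No planned sensitivity analysis for the key secondary endpoints clearly challenges MAR for tezepelumab subjects who stop IP but stay in the study under Option 3

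*SAP*

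**What the plan says.** **Who is missing.** Besides subjects who are lost, die or withdraw consent, SAP 4.2.5.1 states that "subjects who choose Option 3 for their follow-up should be the only source of missing information for the key secondary analyses", with a separate exception for FEV1 under Option 2. Under Protocol 7.1.1, Option 3 means a follow-up visit 16 weeks after the last dose and one contact at Week 52. The same section reserves discontinuation from the study for subjects who refuse all contact, so Option 3 is not study withdrawal.

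**DRMI.** SAP 4.2.5.2 opens with "Missing data will be imputed differently depending on the reason for study withdrawal". Tezepelumab subjects who dropped out for a treatment-related reason get copy reference, "whereas the remaining subjects will be imputed assuming MAR". Table 7, in SAP 4.2.4.2, is limited to tezepelumab subjects withdrawing from the study. The implementation text applies placebo-based imputation to tezepelumab subjects who withdrew for treatment-related reasons. For the others it says that for "all placebo subjects and tezepelumab subjects who withdrew from the study for reasons unrelated to treatment, the imputations are performed assuming MAR". Both tezepelumab groups are therefore defined by withdrawal.

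**Tipping point.** The defining paragraph reads "Tezepelumab subjects who withdrew from the study (irrespective of reason for discontinuing IP) will have their first imputed value worsened by" the chosen amount. Step (ii) then says that, for missing values in the tezepelumab arm, "an imputation model which uses tezepelumab subjects who had observed data at time t will be used, and the one-time worsening" is applied to the result.

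**Supplementary analysis.** SAP 4.2.5.3 repeats the MAR analysis on on-treatment data.

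**The concern.** A withdrawal-based rule suits the primary endpoint. Protocol 7.1.1 has exacerbation information collected by telephone under Option 3, so someone who stays in the study still contributes to the exacerbation count. That does not carry over to spirometry, questionnaires or a diary, which the Week 52 contact does not replace.

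Take two tezepelumab subjects who stop IP for an adverse event, neither with Week 52 data. One then leaves the study and is imputed by copy reference under Table 7. The other accepts a single Week 52 contact and is imputed at MAR, largely from subjects still on drug. Both stopped for the same reason; only willingness to take a call separates them.

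Under a treatment policy strategy, subjects off drug without Week 52 data are where MAR is least secure. A sensitivity analysis meant to test MAR should reach them.

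**Working it through.** **1. The plan's own figures.** Protocol 9.2 and SAP 1.3 give 530 per arm, SDs of 400 mL and 1.3, and differences of 100 mL and 0.3.
- SE = SD × √(2/530): 24.6 mL and 0.0799.
- Power at two-sided 5%: 98.3% for FEV1 and 96.4% for each score. The stated 95% or higher is reproduced.
- Smallest significant difference, 1.96 × SE: 48.2 mL and 0.157, against the stated 50 mL and 0.16.

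**2. How much off-drug data Option 3 supplies.** With last IP at Week X, the 16-week visit falls on Day 7X + 113.
- The Week 52 window in SAP 3.1.5 is Days 351–378. Only X = 36 (Day 365) lands in it; X = 32 gives Day 337 and X = 40 gives Day 393.
- SAP 3.1.5 admits only time points scheduled for the variable. FEV1 from this visit is usable up to Week 52 only for X = 0, 8, 20 or 36, which is 4 of the 12 premature last-dose weeks (0–44).
- AQLQ(S)+12 is not scheduled at that visit, and Option 3 does not require the diary.

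**3. Upper bound on the DRMI change.** Let w be the withdrawn share of the tezepelumab arm, all classed treatment-related, and o the Option 3 share without Week 52 data. Give no credit for earlier values. The estimate is effect × (1 − w) as written, and effect × (1 − w − o) if Option 3 subjects are also imputed from placebo. I take w = 10%, borrowing the dropout rate stated for the primary endpoint; every value of o is assumed.

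| o | Scores, as written | Scores, extended | FEV1, as written | FEV1, extended |
|---|---|---|---|---|
| 2% | 0.270 | 0.264 | 90 mL | 88 mL |
| 5% | 0.270 | 0.255 | 90 mL | 85 mL |
| 10% | 0.270 | 0.240 | 90 mL | 80 mL |

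Significance boundaries with the complete-data SE: 0.166 for ACQ-6 and AQLQ(S)+12 at 3.75%, 48.2 mL for FEV1 at 5%, and 0.157 or about 0.20 for ASD at 5% or 1.25%. If the SE uses only the 80% with Week 52 data at o = 10%, divide by √0.80: 0.186, 54 mL, and 0.223 for ASD at 1.25%. The extended estimates stay above all of these.

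The Option 3 share needed to cross is 1 − boundary/effect − 0.10: about 35% (ACQ-6, AQLQ(S)+12), 42% (FEV1), 38% (ASD at 5%) and 24% (ASD at 1.25%).

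**4. Why the bound is generous.** Copy reference conditions on the subject's own earlier values. Assume compound symmetry with correlation 0.6, the full effect at every observed visit, and baseline plus k post-baseline visits as predictors. The share of the effect lost per subject is then 1/(1 + 0.6k). For AQLQ(S)+12, k over the 12 last-dose weeks is 1, 1, 2, 2, 2, 3, 3, 3, 4, 4, 4, 4. The mean loss is (2 × 0.625 + 3 × 0.455 + 3 × 0.357 + 4 × 0.294)/12 ≈ 0.41.

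With two further assumed patterns (0.9 per 4 weeks; 0.4 + 0.4 × 0.8^(weeks/4)) the ranges are 0.41–0.53 for AQLQ(S)+12, 0.16–0.34 for ACQ-6 and 0.23–0.50 for FEV1. At o = 5%:
- ACQ-6: 0.270 − 0.05 × 0.30 × (0.16 to 0.34) = 0.268 to 0.265.
- FEV1: 90 − 0.05 × 100 × (0.23 to 0.50) = about 89 to 87.5 mL.

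**5. Tipping-point scope.** Assume 5% withdrawn and 5% in Option 3 in each arm, with the one-time shift carried in full to Week 52 (also an upper bound). The largest movement of the difference at the grid corner, shifting withdrawn subjects only or both groups, is 2 × 3 × 0.05 = 0.30 or 0.60 for ACQ-6 and AQLQ(S)+12, 30 or 60 mL for FEV1, and 0.20 or 0.40 for ASD. Scope therefore decides how hard the grid presses.

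**The case against.** Several stronger readings are tempting, and the documents do not support them.

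- **That the SAP is silent on these subjects.** It is not. The primary-endpoint text says "whereas the remaining subjects who dropped out will be imputed assuming MAR", and one might read the same limit into 4.2.5.2. But SAP 4.2.4.1 lists only loss to follow-up, death and consent withdrawal as missing sources, whereas 4.2.5.1 adds Option 3, and 4.2.5.2 uses the wider phrase. A residual class is a rule, and here the rule is MAR. What remains is that the implementation text does not repeat it.
- **That the blinded review cannot reach them.** Its population in SAP 4.2.4.2 is defined by the reason for discontinuing IP, so some Option 3 subjects fall within it. Only the override test is tied to leaving the study: comments must "indicate clearly that the reason for study withdrawal was not related to treatment".
- **That the tipping-point text is evenly ambiguous.** Taken literally, step (ii) covers the whole arm. But the preceding paragraphs speak repeatedly of withdrawal, and step (ii) refers back to a shift already defined. The withdrawn-only reading is clearly the more natural one. It is also the reading that leaves Option 3 subjects unstressed.
- **That key secondary conclusions are at risk.** Step 3 shows otherwise at planning values. At o = 5% the two DRMI versions disagree only if the observed effect lies in 0.185–0.195 (ACQ-6) or 53.5–56.7 mL (FEV1), with a chance of about 2% and 1%.

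It is also fair to say that the extension is a harsher analysis rather than the correction of an error. Every reason for discontinuing IP in Table 7 maps to placebo, three of them by default pending review. SAP 4.2.1 will in any case report how many subjects stayed, by arm and option. These points limit the weight of the concern. They do not supply a challenge to MAR for this group.

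**Conclusion.** The point holds as a minor improvement. SAP 4.2.5.2 applies the primary endpoint's withdrawal-based rule to endpoints for which 4.2.5.1 recognises another kind of missing subject. Tezepelumab Option 3 subjects are imputed at MAR under DRMI. On the natural reading they are not shifted in the tipping-point analysis, and 4.2.5.3 is itself a MAR analysis.

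The size depends on an Option 3 share that the documents do not give. For assumed shares of 2% to 10%, the change in the DRMI estimate is at most 0.006 to 0.03 units or 2 to 10 mL, and probably less because earlier values are used. No DRMI conclusion changes at planning values. The confirmatory MMRM tests, the alpha allocation and the estimand are untouched.

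**What to change.** In SAP 4.2.5.2, define one target set for both DRMI and the tipping-point shifts: subjects with monotone-missing key secondary data who either (a) withdrew from the study, or (b) prematurely discontinued IP and stayed in the study without Week 52 data. Classify group (b) by Table 7's existing column for the reason for discontinuing IP. Have the blinded review in 4.2.4.2 judge that reason, instead of the reason for withdrawal, for group (b). Use the same target-set wording in the tipping-point defining paragraph and in step (ii).

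The cost is a changed subject filter, a few lines of SAP text, a little more blinded review before primary database lock, and slightly less favourable sensitivity estimates. No visit, assessment or data collection changes.
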